8.2.1. Summaries of Adverse Event Incidence Rates for All Subjects

The analysis of TEAEs will be repeated for the following AE categories:

- All AEs sorted by SOC and PT including procedure related AEs
- Procedure related AEs sorted by SOC and PT
- All AEs sorted by SOC and PT excluding procedure related AEs
- All AE's sorted by descending incidence rate in PT
- Serious AEs sorted by SOC and PT
- AE's by severity (mild, moderate, severe) sorted by SOC and PT (A subject with multiple events within a SOC or PT will be reported under the maximum severity) including Procedure Related AEs
- Procedure Related AE's by severity (mild, moderate, severe) sorted by SOC and PT (A subject with multiple events within a SOC or PT will be reported under the maximum severity)
- AE's by severity (mild, moderate, severe) sorted by SOC and PT (A subject with multiple events within a SOC or PT will be reported under the maximum severity) excluding Procedure Related AEs
- AEs by relationship to study medication sorted by SOC and PT (A subject with multiple events within a SOC or PT will be reported under the greatest relationship to study medication)
- AEs leading to study discontinuation sorted by SOC and PT

All listings will be based on the Safety Population and will include all data captured on the eCRF as well as MedDRA information (i.e. SOC and PT). Treatment-emergent AEs will be flagged in this listing. Separate listings will be created for each of the following:

- All AEs
- SAEs
- AEs related to the study medication
- Procedure related AEs
- Serious related AEs
- Severe AEs

- Severe related AEs
- AEs leading to death (i.e. AEs with seriousness, “Death” or outcome “fatal” according on the AE page)
- AEs leading to study discontinuation

A listing with no subjects will display “No Subjects in Listing”.

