8.2. SUBJECT WITHDRAWAL FROM STUDY

Participants may voluntarily withdraw from the study at any time during the course of the study for any reason, specified or unspecified, and without prejudice. The Investigator will document the reason/circumstances for withdrawal in the appropriate eCRF in a timely manner (preferably within 24-48 hours).

Participants can discontinue from the study for any of the following reasons:

- Participants whose MSC or MSC-NTF cells fail to proliferate and to produce a sufficient number of cells for transplantation (see Section 2.1).
- For any reason related to safety or tolerability
- At the subject's request
- At the discretion of the Investigator, if deemed appropriate for any reason
- At the discretion of the Sponsor, if deemed appropriate for any reason

Efforts will be made to have participants who discontinue from the study for any reason, return to the site for an End of Study visit (Visit 7). Such follow-up will include all relevant evaluations for safety and efficacy including clinical assessments and collection of laboratory study results as set out in this protocol.

The subject will be asked if they agree to be followed over the phone at the remaining study visits. If a participant refuses to return for the End of Study follow up visit and declines to be followed with any further clinic visits or assessments, site must document this providing the reason in the End of Study page eCRF in the electronic database. The documentation should include the date the participant withdrew consent/discontinued, the reason for discontinuation, and the fact that the participant refuses to return for the end of study visit. The date documented will be considered the last date of contact and thus the participant's last day on the study.

Despite discontinuing from the study, if the site becomes aware of any adverse events or SAEs that occur within 12 weeks of the last transplant, they should be recorded in the database Adverse Event log

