Abbreviations: MS- Multiple Sclerosis; EDSS-Expanded Disability Status Scale; CSF=cerebral spinal fluid; C-SSRS=Columbia-Suicide Severity Rating Scale; ECG=electrocardiogram; HIV=human immune deficiency virus; HBV=hepatitis B virus; HCV=hepatitis C virus; IT=intrathecal; V=visit, QOL = Quality of Life

*Screening Visits scheduling is coordinated with the manufacturing facility

** If applicable must be repeated within up to 7 days prior to BMA

- 1 MS Medical History to collect type and duration of MS symptoms and Date of Diagnosis
- 2 Pulse rate, Blood pressure (Respiratory rate, Body temperature)
- 3 Hematology: Complete blood count (red blood cells with indices, white blood cells with differential and platelet count, hemoglobin, hematocrit)
- 4 Blood Biochemistry: At V1 and V7: Sodium, potassium, chloride, glucose, BUN, creatinine, bicarbonate, calcium, total bilirubin, AST, ALT, alkaline phosphatase, uric acid, total cholesterol, HDL, LDL. At V3, V4 and V5: sodium, potassium, chloride, glucose, BUN, creatinine
- 5 Coagulation: Prothrombin time (PT), Partial thromboplastin (PTT), INR.
- 6 Urinalysis - Specific Gravity, pH, glucose, protein, ketones, blood.
- 7 EDSS-Expanded Disability Status Scale.
- 8 MSFC including T25FW and 9-HPT (9-hole peg test)
- 9 Symbol Digit Modalities Test (SDMT).
- 10 12 item MS Walking Scale (MSWS-12).
- 11 An Early Termination (ET) visit will be conducted only for participants who discontinue the study after the first treatment, post Visit 3. The ET visit will include all the procedures required at study Visit 7.
12. A more flexible window may be applied to the key study visits, BMA (V2), T1 (V3), T2 (V4) and T3 (V5) that are scheduled based on manufacturing availability

Brainstorm Cell Therapeutics Ltd.	IND#018615	
Phase 2 Clinical Protocol BCT-101-US Amendment 1.1, June 2019	MSC-NTF cells (NurOwn®)	Page 54 of 59

Table 2. Detailed Schedule of Assessments for Cell Transplantation Visits (V3, V4, and V5)

Estimated Time	xx:00-yy:00**	14:00	20:00	8:00	12:00
Time\ Procedure	Up to 8 hours before transplant	Hr. 2	Hr. 8	Hr. 20	Approximately Hr. 24/Discharge
Admit to In-patient Facility	√				
Physical Examination	√				√
Concomitant medication review	√				√
Hematology ^{1*}	√				
Blood biochemistry ^{2*}	√				
Coagulation ^{3*}	√				
Blood collection for biomarkers	√				√
Vital signs ⁴	√	√	√	√	√
Adverse events review	√	√	√	√	√
Cell Transplant IT					
Retention of CSF sample					
Visual inspection of injection site		√			√

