6.5. Analysis Populations

6.5.1. Safety Population

All safety analyses will be conducted on the Safety Population, which is defined as all participants who were enrolled, and had at least one transplantation performed.

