7. STUDY POPULATION

7.1. Subjects Disposition

Subject disposition will be summarized descriptively as follows:

- A summary of the number of subjects in each of the analysis populations.
- The number and percentages of subjects who signed informed consent but were not treated.
- The number and percentages of subjects who had Bone Marrow Aspiration but were not treated.
- The number and percentage of subjects who (a) completed study (b) discontinued from the study by number of treatments prior to discontinuation. For those who discontinued from the study, the primary reason for discontinuation from the study will be presented.
- If any subjects are re-screened this will be footnoted in the Table along with the Subject-ID.

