8. SAFETY AND TOLERABILITY

All safety analyses will be based upon the Safety Population.

All AEs will be coded to SOC and PT using the MedDRA, version 21.1.

A Treatment-emergent adverse event (TEAE), referred to subsequently as just TEAE or AE is an AE that occurs for the first time after initiation of first treatment or if it had occurred prior to initiation first treatment, it worsens in severity after initiation of first treatment.

AE's that occur prior to initiation of first treatment will only be in the listings and not included in any summary Tables.

AE's related to the Bone Marrow Aspiration will be included in a separate listing.

When evaluating changes in continuous safety parameters (such as laboratory measurements, vital signs, ECGs, etc.) , Baseline will be defined as the last measurement prior to first transplantation (i.e., prior to initiation of treatment).

Additional details for analysis of safety data are detailed below.

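### As SAP 8.2.1 is written, adverse events in participants aspirated but never treated would reach no AE table and none of its listings; other SAP sections conflict with this or leave it unclear

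*SAP*

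**What the plan says.** **Population.** SAP 6.5.1 defines the Safety Population as "all participants who were enrolled, and had at least one transplantation performed". SAP 8 bases all safety analyses on it, and SAP 8.2 uses it as the denominator for AE percentages.

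**Listings.** SAP 8.2.1 says: "All listings will be based on the Safety Population and will include all data captured on the eCRF". It then names nine listings, including all AEs, SAEs, procedure-related AEs and AEs leading to study discontinuation.

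**Events before first treatment.** SAP 8 says: "AE's that occur prior to initiation of first treatment will only be in the listings and not included in any summary Tables". It adds: "AE's related to the Bone Marrow Aspiration will be included in a separate listing". No population is given for that aspiration listing, and it is not one of the nine.

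**Who is aspirated but not treated.** SAP 7.1 plans to count "subjects who had Bone Marrow Aspiration but were not treated". Protocol 2.1 has participants told at consent that they may not be transplanted if their cells do not grow sufficiently, and Protocol 8.2 makes this a reason to discontinue.

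**Collection.** Under Protocol 7, AEs and SAEs are collected from consent, and Protocol 7.1.1 includes procedure-related observations.

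**The concern.** The product is autologous, so nobody can be dosed without the aspiration: 80 to 100 mL taken bilaterally from the iliac crest through multiple punctures (Protocol 2.3.1), about five to six weeks before the first dose (Protocol 4.6.2). Protocol 6.3 itself treats it as a procedure that carries bleeding risk under anticoagulation.

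The primary objective is safety, and the data are meant to inform a future randomized study whose participants would presumably face the same procedure. The natural denominator for aspiration-related harm is everyone aspirated. The SAP instead conditions its AE listings on a later event, receipt of a dose. The plan already expects that some participants may not reach it, and it counts them in disposition without stating where their adverse events are shown.

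**Working it through.** The documents give no figure on this point, so there is none to reproduce. The check is of text against text, followed by an illustration of scale.

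**Step 1: follow one participant through the plan.** Take someone aspirated at Visit 2 who never receives a first dose.

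- Events recorded? Yes, from consent (Protocol 7).
- In the Safety Population? No (SAP 6.5.1).
- In an AE summary table? No, on two counts: outside the Safety Population (SAP 8, 8.2), and the events precede first treatment (SAP 8).
- In one of the nine 8.2.1 listings? No, as that section is written.
- In disposition? Yes, as a count, with the primary reason for discontinuation (SAP 7.1), but without adverse events.

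For a participant who is later dosed the result differs. Aspiration events are listed, but not tabulated.

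**Step 2: set the other passages beside 8.2.1.**

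| Place | What it implies for this participant |
|---|---|
| SAP 6.1 | Listings cover all safety data collected, with an exception only for activity-watch data: included |
| SAP 8.1 | The AE listing is complete with respect to the CRF: included |
| SAP 8.2.1 | AE listings use the Safety Population: excluded |
| SAP 8, aspiration listing | No population stated: unclear |
| SAP Appendix 4.1, AEs of subjects who discontinued the study because of an AE | No population stated: unclear |

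The first three rows cannot all hold. The last two depend on whether the 8.2.1 rule extends to them. The Appendix listing, even read broadly, would miss AEs in someone who left because the cells failed to grow.

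**Step 3: scale, under assumptions.** Assume 20 are aspirated and m of them are never treated. The documents give no m, nor do they say whether the planned 20 counts aspirated or treated participants. The share omitted is m/20. If each has the same independent risk p of an aspiration-related event, the chance that at least one such event falls in an omitted participant is 1 − (1 − p)^m. For m = 2 and p = 0.10 this is 1 − 0.90² = 0.19.

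| m | Share omitted | p = 5% | p = 10% | p = 20% |
|---|---|---|---|---|
| 0 | 0% | 0% | 0% | 0% |
| 1 | 5% | 5.0% | 10.0% | 20.0% |
| 2 | 10% | 9.8% | 19.0% | 36.0% |
| 4 | 20% | 18.5% | 34.4% | 59.0% |

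A single SAE among 20 aspirated is 1/20 = 5.0% (exact 95% interval 0.1% to 24.9%). If that participant is not dosed, a display restricted to the treated shows 0/19, with exact upper limit 1 − 0.025^(1/19) = 17.6%. In an extreme case, with m = 4 and events in all four untreated and no one else, it shows 0/16 (upper limit 1 − 0.025^(1/16) = 20.6%) when the experience is 4/20 = 20%.

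**The case against.** The strongest reply is that the SAP already promises the data elsewhere: SAP 6.1 and 8.1 are broad, the aspiration listing stands outside the nine in 8.2.1, and the Appendix adds a listing for those who left because of an AE. This stands in part. It means that omission is one reading of inconsistent wording. It does not remove the problem, because neither broad sentence mentions untreated participants and 8.2.1 is the specific rule for AE listings.

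A second reply is that the primary objective concerns three intrathecal doses, so a treated population and treatment-emergent tables fit it, and listing pre-treatment events was a deliberate choice. This also stands in part: those tables need not change, and at this sample size a full breakdown by system organ class and preferred term would be largely a matter of preference.

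Three stronger readings are tempting and are not supported:

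- **That aspiration harm goes unrecorded or unseen.** AEs are collected from consent, and SAP 5.2 sends serious AEs to the DSMB monthly and deaths as the sponsor learns of them.
- **That an aspiration SAE ending participation could appear nowhere in the report.** The aspiration listing and the Appendix discontinuation listing may cover it; their scope is unstated.
- **That those most likely to be harmed are removed, so the aspiration looks safer than it is.** An aspiration complication could prevent dosing, but the specific reason the protocol names for not reaching the first dose is cell-growth failure. Nothing in the documents links that to aspiration events, and the number untreated is not given.

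**Conclusion.** The point holds as a gap and an inconsistency in planned reporting. Under SAP 8.2.1 read with 6.5.1 and 8, adverse events in a group the plan itself foresees would be in no AE table and none of the 8.2.1 listings. SAP 6.1 and 8.1 say otherwise, and two further listings leave the matter open.

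The size is unknown and could be nil if everyone aspirated was treated. On the assumption of 20 aspirated, each untreated participant is 5% of those exposed; the event risks in the second table are illustrative. The intervals for 1/20 and 0/19 overlap heavily, so the gain from correction is completeness of the primary safety report rather than precision. Neither the direction nor the amount of any bias can be established from the documents.

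One separate inconsistency concerns the same participants. Protocol Table 1, footnote 11, says: "An Early Termination (ET) visit will be conducted only for participants who discontinue the study after the first treatment, post Visit 3". Protocol 8.2 instead seeks a Visit 7 after discontinuation for whatever reason. This bears on the exit assessment, not on whether recorded events are displayed.

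**What to change.** 1. In SAP 6.5, define an aspirated set: all participants who had a BMA, treated or not.
2. In SAP 8, 8.2.1 and Appendix 4.1, base the aspiration-related AE listing, the pre-treatment AE and SAE listings and the discontinuation-AE listing on that set. This also brings 8.2.1 into line with SAP 6.1 and 8.1.
3. Report the number and percentage with any aspiration-related AE, and with any aspiration-related SAE, before first treatment, with all aspirated as denominator.
4. Leave the treatment-emergent tables on the Safety Population.
5. Separately, reconcile Protocol Table 1, footnote 11, with Protocol 8.2 for participants who leave between aspiration and first treatment.

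The cost is one population flag, a short summary from data already collected, and SAP wording. The safety profile may look slightly less favourable.

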8.3. Routine Laboratory Data

The analyses of the safety laboratory will be performed using the Safety Population. Multiple assessments within a visit or time interval will be handled as described in [Section 6.7.4](#).

Mean Changes and % Changes from baseline to each post baseline timepoint in each laboratory assessment that is a continuous variable will be summarized along with other descriptive statistics for continuous variables.

Additionally, chemistry and hematology parameters will be categorized as low, normal or high according to laboratory range specifications. In addition, Investigator assessment of whether the abnormality was clinically significant will be recorded.

The number and percentage of subjects will be presented at each assessment time point for the safety population using the following categories:

- missing data
- clinically significant low abnormality
- non-clinically significant low abnormality
- normal values
- non-clinically significant high abnormalities
- high clinically significant abnormalities

In addition shift Tables will summarize clinically significant abnormalities between baseline and post baseline value using the above categories and the worst values post baseline. Note, this tabulation is not by visit.

Urinalysis tests that are recorded as continuous parameters like pH and specific gravity will be analyzed as above. All other urinalysis parameters will just be included in the listings.

Coagulation parameters will be analyzed as above.

Laboratory values outside the normal range will be displayed in a separate listing with clinically significant values flagged. Determination of clinical significance will be made by the Investigator and recorded in the eCRF.

Laboratory parameter units will be standardized to conform to the Table below:

Laboratory parameters for safety investigations will be analyzed in the standardized units given below:

Blood Biochemistry:

• Alkaline phosphatase	U/L
• Alanine aminotransferase (ALT)	U/L
• Aspartate aminotransferase (AST)	U/L

BrainStorm Cell Therapeutics Ltd.
Statistical Analysis Plan - Protocol BCT-101-US

April 12, 2019

• Bicarbonate	mmol/L
• Blood urea nitrogen (BUN)	mg/dL
• Calcium	mmol/L
• Chloride	mmol/L
• Creatinine	µmol/L
• Glucose	mmol/L
• High-Density Lipoprotein (HDL) Cholesterol	mmol/L
• Low-Density Lipoprotein (LDL) Cholesterol	mmol/L
• Potassium	mmol/L
• Sodium	mmol/L
• Total Bilirubin	µmol/L
• Total Cholesterol	mmol/L
• Uric Acid	mg/dL

Hematology:

• Basophil Differential	%
• Basophils (Absolute)	10 ⁹ /L
• Eosinophil Differential	%
• Eosinophils (Absolute)	10 ⁹ /L
• Erythrocytes (RBC)	10 ¹² /L
• Hematocrit	Fraction
• Hemoglobin	g/L
• Leucocytes (WBC)	10 ⁹ /L
• Lymphocyte Differential	%
• Lymphocytes (Absolute)	10 ⁹ /L
• Monocyte Differential	%
• Monocytes (Absolute)	10 ⁹ /L
• Neutrophil Differential	%
• Neutrophils (Absolute)	10 ⁹ /L
• Platelets	10 ⁹ /L

Coagulation:

• Prothrombin Time (PT)	sec
• Partial Prothrombin Time (PPT)	sec
• International Normalized Ratio (INR)	

8.4. Vital Signs

Mean Changes and % Changes from baseline to each post baseline timepoint in each Vital Signs assessment will be summarized along with other descriptive statistics for continuous variables.

Additionally, vital signs parameters will be categorized as low, normal or high according to the following ranges for clinically notable vital sign abnormalities

VITAL SIGNS		NOTABLE ABNORMALITIES Change Relative to baseline or Absolute Levels
Pulse (beats/min)		Either ≥ 120 + increase ≥ 15 or > 130 Either ≤ 50 + decrease ≥ 15 or < 40
Blood pressure (mmHg)	Systolic	Either ≥ 180 + increase ≥ 20 or > 200 Either ≤ 90 + decrease ≥ 20 or < 75
	Diastolic	Either ≥ 105 + increase ≥ 15 or > 115 Either ≤ 50 + decrease ≥ 15 or < 40
Weight		Either \leq or $\geq 10\%$ -

8.5. Physical Examination

Physical exam abnormalities will be displayed in a listing.

8.6. 12-Lead Electrocardiogram

No analyses of 12-Lead ECG parameters will be performed since it is conducted only at screening visit. A listing by subject will be presented.

8.7. MRI analysis

MRI Data will be analyzed for safety by looking at the following change from baseline to end of study:

- Mean Changes in number of new or enlarging FLAIR lesions on MRI
- Percentage of subjects with $\geq 1, \geq 2, \geq 3$ new or enlarging FLAIR lesions on MRI
- Mean Changes in active FLAIR lesions (new + enlarging) on MRI
- Percentage of subjects with $\geq 1, \geq 2, \geq 3$ active FLAIR lesions (new + enlarging) on MRI
- Mean Change in Total volume of new FLAIR lesions on MRI
- Mean Change in Total volume of FLAIR lesions on MRI

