4.2. MRI

Standard MRI technologies will be used for T1 and T2 weighted imaging analyses. MRI data will be inspected and deidentified, as necessary, by an independent person who will not be involved in the research or analysis of the data. Brain MRI scan will be read and compared to previous MRI scans.

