6.7.3. Change from Baseline

Change from baseline is calculated as (post-baseline result – baseline result).

Percent change from baseline is calculated as (change from baseline/baseline result)*100 as long as baseline is non-zero. If baseline is 0, change from baseline is defined as missing.

If either the baseline or the post-baseline result is missing, the change from baseline and/or percentage change from baseline is set to missing as well.

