5.4 MRI

MRI data will also be analyzed for efficacy. Continuous data will be analyzed as changes from baseline and categorical data by counts and percentages.

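### Three of the six MRI measures in SAP 8.7 subtract a baseline value from a quantity that is already a between-scan change, and no reference scan for that baseline value is defined

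*SAP*

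**What the plan says.** SAP 8.7 introduces its six MRI measures with "MRI Data will be analyzed for safety by looking at the following change from baseline to end of study". Four of the six are then worded as changes. For lesion number the SAP writes "Mean Changes in number of new or enlarging FLAIR lesions on MRI", and it uses the same form for active lesions, which it defines as the new and the enlarging ones taken together. For volume it writes "Mean Change in Total volume of new FLAIR lesions on MRI", and it lists a further change measure for the volume of all FLAIR lesions, old and new alike.

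The other two are percentages of subjects with at least 1, 2 or 3 new or enlarging lesions, and the same for active lesions. They carry no change wording of their own.

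SAP 6.7.3 gives the general rule: "Change from baseline is calculated as (post-baseline result" minus the baseline result. It sets the change to missing if either value is missing. SAP 6.8 imputes nothing except dates.

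The schedules of assessments in both documents place MRI at Visit 1 and Visit 7 only. On reading the scans, Protocol 4.2 says "Brain MRI scan will be read and compared to previous MRI scans". It does not say which earlier scan is meant, does not require one before Visit 1 and sets no age limit.

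Appendix I to the SAP, section 5.4, adds MRI as an efficacy analysis: "Continuous data will be analyzed as changes from baseline and categorical data by counts and percentages".

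**The concern.** A new or enlarging lesion exists only relative to an earlier scan. At Visit 7 the natural reference is Visit 1. At Visit 1 there is no earlier study scan, so a baseline number of new lesions would need a scan from before the study. Subtracting that number from the Visit 7 number sets lesions gathered over one interval against lesions gathered over another, unrelated interval.

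MRI data are part of the primary safety endpoint (SAP 3.2.1), and the study has no concurrent control against which a distorted mean could be recognised. A mean that can move down or up with no change in lesion activity is a poor safety summary. The same mean could also enter the efficacy analysis through Appendix I 5.4.

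**Working it through.** The documents give no lesion rate, variance or threshold for MRI, so there is no planned figure to reproduce. The check has two parts.

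**1. Which measures are affected**

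| Measure in SAP 8.7 | Already a between-scan change? | Effect of applying 6.7.3 |
|---|---|---|
| Mean change, new or enlarging lesions | Yes | Needs an undefined Visit 1 value |
| Mean change, active (new + enlarging) lesions | Yes; same quantity as the row above | Same |
| Mean change, volume of new lesions | Yes | Same |
| Percentage with at least 1, 2, 3 lesions (two measures) | Yes | None, if Visit 1 is the reference |
| Mean change, total FLAIR lesion volume | No; measured on each scan | Valid: Visit 7 minus Visit 1 |

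**2. What the subtraction does if a pre-study scan is used**

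Inputs from the documents:
- Screening to first treatment: 6 to 10 weeks (Protocol synopsis and 2.1).
- First treatment to Visit 7: 28 weeks (schedule of assessments).
- On-study interval S = (6 to 10) + 28 = 34 to 38 weeks. Divided by 52.18, this is 0.652 to 0.728 years.
- Number of patients: 20.

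Assumptions, not given in the documents:
- New lesions arise at a constant rate L per patient-year (Poisson).
- The pre-study scan is T years before Visit 1 in every patient.

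Formulas:
- Expected Visit 1 count = L × T.
- Expected Visit 7 count = L × S with no treatment effect, or 2 × L × S if treatment doubles the rate.
- Expected change = L × (S − T) with no effect, or L × (2S − T) with a doubled rate.

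With no effect the expected change is zero only when T = S. It is negative for T above 0.65 to 0.73 years and positive below. With a doubled rate it is still negative once T exceeds 2S = 1.30 to 1.46 years.

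With L = 0.5 (for example, T = 2 and S = 0.728: 0.5 × (0.728 − 2) = −0.64), and the chance of a negative mean in 20 patients found by simulation:

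| T (years) | Change, no effect (S = 34 / 38 weeks) | Chance mean < 0 | Change, rate doubled | Chance mean < 0 |
|---|---|---|---|---|
| 0.25 | +0.20 / +0.24 | 6% / 4% | +0.53 / +0.60 | 0.1% / under 0.1% |
| 0.5 | +0.08 / +0.11 | 28% / 21% | +0.40 / +0.48 | 2% / 1% |
| 1 | −0.17 / −0.14 | 77% / 70% | +0.15 / +0.23 | 23% / 15% |
| 2 | −0.67 / −0.64 | 99% / 99% | −0.35 / −0.27 | 87% / 80% |

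The result scales with L. At T = 2 and no effect, L = 0.1 gives about −0.13 and L = 1.0 gives −1.35 / −1.27.

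A patient with no pre-study scan has no Visit 1 value. SAP 6.7.3 then sets the change to missing, and the patient drops out of all three measures.

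**Counting once, Visit 7 against Visit 1.** T disappears. At L = 0.5 the expected count is 0.33 to 0.36 lesions per patient with no effect and 0.65 to 0.73 if the rate doubles. It cannot be negative.

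**The case against.** The strongest reply is that the SAP means something simpler. The opening line of 8.7 can be read as new lesions between baseline and end of study. The percentage measures make plain sense only that way, and with scans at just two visits the obvious count is Visit 7 against Visit 1. Neither document plans a new-lesion count at Visit 1 or collects a pre-study scan. Protocol 4.2 is a general reading instruction that a Visit 7 against Visit 1 comparison also satisfies. On this view the change wording is only clumsy, and scan age plays no part.

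Much of that stands, and this may well be the intended reading. It does not remove the need for a correction. In the same list the words for total FLAIR lesion volume must mean Visit 7 minus Visit 1, and nothing gives the similar words beside it another meaning. Appendix I 5.4 repeats the rule for continuous MRI data, though without naming new-lesion counts. No sentence names Visit 1 as the reference, so a programmer following 6.7.3 would subtract or produce missing values.

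It is also fair to say that the percentages and total lesion volume would still show new activity, and that SAP 6.1 requires listings of all safety data for each subject. With 20 patients, individual results stay visible.

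**Conclusion.** The defect is real for three of the six measures. As written, their definition gives either a missing value or a value that depends on an unspecified pre-study scan. If such scans are used, the distortion runs both ways: a false decrease with scans older than about 34 to 38 weeks before Visit 1, a false increase with more recent ones. The direction rests on a constant lesion rate, and the size on rates and scan ages that the documents do not supply. The tabulated values are therefore illustrations, not forecasts for this trial.

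A reader might go further and infer that the MRI safety result does depend on pre-study scans, that it leans towards apparent improvement, or that MRI safety as a whole is unreliable. The documents do not support any of these. They plan no Visit 1 new-lesion count, the bias has no fixed direction, and the remaining measures are sound on the conditions given above. This should be fixed as a matter of definition. It does not undermine the study.

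**What to change.** In SAP 8.7, and in Appendix I 5.4 wherever these measures are used:

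1. State that new or enlarging lesions, and their volume, are determined on the Visit 7 scan against the Visit 1 scan.
2. Report them directly, with no Visit 1 value subtracted: mean and median for number and volume, and the percentage of subjects with at least 1, 2 and 3 lesions.
3. Merge the new-or-enlarging and active measures, which are the same quantity.
4. Keep change from baseline for total FLAIR lesion volume only.

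The cost is a few lines of SAP text and simpler programming. No scans beyond Visit 1 and Visit 7 are needed. The documents imply but do not state outright that Visit 7 is read against Visit 1, so this should be confirmed with whoever reads the scans. If it was not done, at most 20 pairs of scans need that comparison.
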